1.5.6. Additional analysis for ADNEX

We will further analyse the ADNEX predictions in terms of discrimination and calibration. First, c-statistics between each pair of outcome categories will be computed using the conditional method (Van Calster, 2012). Only pooled results will be shown (i.e. no meta-analysis) because some outcome categories will have few events in several centers. For imputed data, logit(AUC) will be computed for each imputation, and combined using Rubin Rules.

Second, multinomial logistic calibration curves will be constructed (Van Hoorde 2014). For imputed data, curves will be derived per imputed dataset, and averaged.

1.5.7. Subgroup analyses

We will compute the overall c-statistic for benign vs malignancy (i.e. after meta-analysis) and overall calibration curves for the following prespecified subgroups:

- By actual management: separate analysis of patients who were operated within 120 days after the first scan and without follow-up scan (similar to the population for the IOTA1-4 studies), and patients who received at least 1 follow-up scan; note that not all recruited patients fall within one of these two categories
- By suggested management ('intention to treat'): separate analysis of patients with suggested management surgery and patients with suggested management conservative
- By menopausal status: separate analysis of premenopausal patients and postmenopausal patient separately
- By type of center: separate analysis of patients examined in oncology centers and patients examined in other centers

The analysis of these subgroups will be done on data from the main centers, using meta-analysis if numbers allow. If numbers (e.g. number of patients with a malignancy) per center are too small, pooled analysis will be done.

No subgroup analyses are planned for the additional assessment of multinomial discrimination and calibration of the ADNEX model.

1.5.8. Sensitivity and supplementary analyses

The following sensitivity or supplementary analyses will be performed. For each analysis, we will report overall c-statistics for benign vs malignancy (i.e. after meta-analysis), as well as overall calibration curves.

- The 18 excluded centers (BIT, PCR, LPO, CAI, CEG, CRI, UDI, BAI, BCH, FIT, KPO, LIP, MCA, MFR, PCR, PFR, RZT, VAS) will be included in a supplementary analysis of performance in masses that are operated without follow-up (within 120 days after inclusion). This analysis will therefore include all centers: the 17 main centers listed above, and the 18 excluded centers. For this analysis, a separate multiple imputation procedure will be used.
- Sensitivity analysis where patients with an uncertain outcome as listed above (groups U1-U4 from section 1.3) are excluded rather than imputed.
- Sensitivity analysis after imputation of the outcome for all patients for which the outcome was uncertain or determined using subjective assessment (groups U1-U4, B2, N2, M3 from section 1.3).

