management and % useful info): AGR, CIT, DEP, FLI, GBE, IUK, LBE, MIT, MPO, MSW, NCI, NUK, OIT, PSP, RIT, SIT, SSW, TIT and TUS.

1.2 Analysis:

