1.3 Data

The IOTA5 database will be used for the analysis and the following in- and exclusion criteria will be used.

Inclusion criteria:

- Recruitment scan between 1 January 2012 and 1 March 2015.
- Patients who were not already in follow-up at a center before the recruitment scan ('new' patients) (i.e. new patients)
- Patients recruited in centers AGR (Athens), CIT (Milan), FLI (Florence), GBE (Genk), IUK (London), LBE (Leuven), MIT (Milan), MPO (Katowice), MSW (Malmö), NCI (Milan), NUK (Nottingham), OIT (Monza), PSP (Pamplona), RIT (Rome), SIT (Cagliari), SSW (Stockholm), TIT (Trieste). i.e. centers with 'good' follow-up data and surgery data. The are the 'main centers'.

- Other centers (BIT, PCR, LPO, CAI, CEG, CRI, DEP, UDI, BAI, BCH, FIT, KPO, LIP, MCA, MFR, PFR, RZT, TUS, VAS) will be included in a supplementary analysis of performance in masses that are operated without follow-up (within 120 days after inclusion), together with the main centers. See below.

Exclusion criteria:

- Patients who did not give consent; data from patients who withdrew consent during the study will not be used either
- Younger than 18 years at first scan
- Patients who were already in follow-up at a center before the recruitment scan ('new' patients) (i.e. old patients)
- Cysts that are deemed clearly physiological if less than 3 cm in maximum diameter are not eligible for inclusion.

Multiple masses:

When the examiner detected multiple masses, the mass with the most complex ultrasound morphology was defined as the dominant mass. If multiple masses had similar morphology, the largest mass or the one best accessible with ultrasound was denoted as dominant.

Outcome:

Some patients received surgery without follow-up, some received follow-up only, some received follow-up with surgery later on, and for some patients we did not know what happened after the inclusion visit. We determine the dichotomous outcome (benign or malignant tumor) using the following rules:

- A. If surgery, irrespective whether there was FU or not:
 - If the resulting histology was benign: classify as *benign (B1)*
 - If the resulting histology was malignant:
 - o If surgery was within 120 days from the inclusion visit: classify as *malignant at inclusion (M1)*
 - o If surgery was >120 days after the inclusion visit, but subjective assessment was probably or certainly malignant (including borderline) at every visit: classify as *malignant at inclusion (M2)*

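### The supplementary analysis meant to cover all centres lists 17 distinct excluded centres, counts them as 18, and leaves out DEP and TUS, which section 1.3 includes

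*SAP*

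**What the plan says.** Two sections of the model-performance part of the SAP define the centres for the same supplementary analysis.

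- **Section 1.3 (Data)** first names the main centres: "AGR (Athens), CIT (Milan), FLI (Florence), GBE (Genk), IUK (London), LBE (Leuven), MIT (Milan), MPO (Katowice), MSW (Malmö), NCI (Milan), NUK (Nottingham"), followed by "OIT (Monza), PSP (Pamplona), RIT (Rome), SIT (Cagliari), SSW (Stockholm), TIT (Trieste"). It then names the rest: "Other centers (BIT, PCR, LPO, CAI, CEG, CRI, DEP, UDI, BAI, BCH, FIT, KPO, LIP, MCA, MFR, PFR, RZT, TUS, VAS"). Of these it says that they "will be included in a supplementary analysis of performance in masses that are operated without follow-up (within 120 days after inclusion), together with the main" centres.
- **Section 1.5.8 (Sensitivity and supplementary analyses)** gives the added centres as "The 18 excluded centers (BIT, PCR, LPO, CAI, CEG, CRI, UDI, BAI, BCH, FIT, KPO, LIP, MCA, MFR, PCR, PFR, RZT, VAS"). It goes on: "This analysis will therefore include all centers: the 17 main centers listed above, and the 18 excluded centers". It also says that this analysis gets its own multiple imputation, and that overall c-statistics and overall calibration curves will be reported.

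The follow-up part of the SAP (27 December 2017), section 1.1, has its own list of centres for its primary analysis. That list begins "AGR, CIT, DEP, FLI" and ends with TUS, so both DEP and TUS were primary-analysis centres there.

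**The concern.** The list in section 1.5.8 does not match its own label or the list in section 1.3. It repeats one code and lacks two others. DEP and TUS are not main centres in the 2019 plan, so under 1.5.8 they fall into no group at all, although the text says that every centre is covered.

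The list defines an analysis population. The pooled AUC comes from a random-effects meta-analysis in which each centre is a unit (section 1.5.3), so the choice of centres decides what enters the estimate. It also decides whose data feed the separate imputation. An analyst who programs from 1.5.8 and one who programs from 1.3 would build different datasets, and the SAP does not say which is intended. The plan is dated after the 30 June 2017 follow-up cut-off, so centre selection should leave no room for choice.

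**Working it through.** This is a count and a comparison of centre codes. No statistical formula is involved.

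**Inputs**

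| List | Source | Entries | Distinct codes | DEP and TUS present? |
|---|---|---|---|---|
| Main centres | Model performance, 1.3 | 17 | 17 | No |
| Other centres | Model performance, 1.3 | 19 | 19 | Yes, both |
| Excluded centres | Model performance, 1.5.8 | 18 | 17 (PCR twice) | No |
| Primary-analysis centres | Follow-up study, 1.1 | 19 | 19 | Yes, both |

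**Step 1: reproduce the stated figures.** The 17 main centres reproduce exactly. The figure of 18 excluded centres is reached only by counting PCR twice: 18 entries − 1 duplicate = 17 distinct centres.

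**Step 2: compare the two lists of added centres.**
- In 1.3 but not in 1.5.8: DEP and TUS.
- In 1.5.8 but not in 1.3: none.
- Check: 19 − 2 = 17, the distinct count found in step 1.

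**Step 3: check for overlap.** No main centre appears in either list of added centres, so the counts can simply be added.

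**Step 4: totals for the analysis.**
- As listed in 1.5.8: 17 + 17 = 34.
- As stated in 1.5.8 ("the 17 main centers listed above, and the 18 excluded centers"): 17 + 18 = 35.
- As listed in 1.3: 17 + 19 = 36.

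No two agree. Deleting the second PCR does not reconcile the sections, because 17 still differs from 19.

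**Step 5: size.** The centres at issue are 2 of 36, and 2 / 36 = 5.6%. Against the section 1.3 total, the centre count would be wrong by 36 − 35 = 1 if the stated total were reported, and by 36 − 34 = 2 if the listed codes were used.

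**A possible origin.** The 19 primary centres of the 2017 follow-up part are the 17 main centres of the 2019 part plus DEP and TUS. The 17 distinct codes in 1.5.8 are the centres of the 36 that lie outside that 2017 list (36 − 19 = 17). This pattern would arise if the list in 1.5.8 was not updated when DEP and TUS left the main set. It is an inference; the documents do not say so.

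**The case against.** The mismatch itself cannot be argued away: nothing elsewhere in the SAP reconciles the two lists, and no redaction or extraction fault explains them. The case on the other side is about how much it matters.

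- **The intent is readable.** Both sections point to an analysis over all centres. A programmer who reads the whole SAP would meet the conflict and probably ask, and a repeated code has no effect on a data selection. This is fair. The loss of two centres is therefore conditional on 1.5.8 being followed literally. But the SAP should not depend on a programmer noticing.
- **The size is in centres, not patients.** The documents give no number of patients, malignancies or early operations for DEP or TUS. The effect on the estimates could be nil. This stands: 5.6% is a share of centres and nothing more.
- **Their place in the follow-up study proves little here.** Those centres were chosen on numbers recruited for conservative management and the share with useful information. The 2019 main centres also needed good surgery data, and DEP and TUS are not among them. This stands as well. Their 2017 status does not show that they belong in an analysis of operated masses. What puts them there is section 1.3, which names them for it.
- **The omission may be deliberate.** The documents do not rule this out. If it is, 1.3 and the claim to cover all centres are wrong instead, and a correction is still needed.
- **Only a supplementary analysis is touched.** Correct. This limits the severity but does not remove the contradiction.

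**Conclusion.** The concern holds. Section 1.5.8 labels 17 distinct centres as 18 and omits DEP and TUS, which section 1.3 assigns to the same analysis. The total is 34, 35 or 36 depending on which statement is followed.

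If 1.5.8 is programmed literally, 2 of 36 centres (5.6%), with any of their patients operated within 120 days without follow-up, drop out of the analysis and of its imputation, while the analysis is described as complete. The figure of 36 rests on the two lists in section 1.3, since no section states the number of recruiting centres. The effect on the c-statistics and calibration cannot be judged from the documents.

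The primary model-performance analysis and the subgroup analyses use the 17 main centres, which are listed and counted consistently, and are not affected. This should be corrected, but it does not threaten the main result.

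**What to change.** Make sections 1.3 and 1.5.8 of the model-performance part agree on one list and one count.

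- **If DEP and TUS belong in the analysis,** as section 1.3 says: replace the list in 1.5.8 with the one in 1.3, with PCR once and DEP and TUS added. Change 18 to 19 and give the total as 36.
- **If they were left out on purpose:** remove them from the corresponding sentence in 1.3, give the reason, correct the count in 1.5.8 to 17 (34 in total), and stop describing the set as all centres.

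In either case, define the separate imputation on the same list, and check the final list against the centre codes in the database.

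The cost is one corrected list and two numbers in the SAP, plus a sentence of justification if the centres are excluded. If the analysis has already been run, the centre codes in the analysis file show which version was used. A rerun is needed only if that differs from the agreed list.

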This is an observational study and therefore a sample size cannot be calculated. We aim to collect at least 3000 women with an adnexal mass and at least 1000 women with an adnexal mass managed conservatively. We plan an initial recruitment period of eighteen months. Patients will be followed up for at least 5 years, unless surgical intervention is necessary.

Follow-up

Ultrasound (and clinical) follow up will be organised by the ultrasound examiner who entered the patient into the study. Follow-up will be after 3 months (maximal range 1-4 months), 6 months (maximal range 4-8 months) and then every 12 months (maximal range 10-14 months). Although measurement of serum CA 125 levels is encouraged, it is not mandatory for inclusion in the study. If CA125 is measured it should be recorded in the study screen and preferably measured on each visit.

Duration of follow-up

A yearly analysis will be carried out in order to evaluate acute complications. The duration of follow up will be for at least 5 years and is not limited as long as the patient is compliant with the study and the study is ongoing.

Departments (e.g. radiology departments) that are not involved with clinical decision making about plans for follow up or surgery cannot participate in the full IOTA 5 study. In these centres data can be prospectively collected as an observational study. Only patients with appropriate outcome measures (i.e. follow up ultrasonography after one or more years or patients with complete details of clinical history or surgical procedures) will be included in any statistical analysis.

Collection of clinical data

Family history: Number of first degree relatives with ovarian cancer (0-...)

Medical history:	Personal history of ovarian cancer and breast cancer
	Age (years)
	Previous hysterectomy (yes/no)
	Previous oophorectomy (yes/no)
	Contraception (drop down list) (None/oral combined contraceptive
	pill/progestogen only pill/ patch/vaginal ring/Mirena coil/copper IUD)
	Hormonal therapy (yes, no).
	Is the patient currently wishing to conceive? (yes/no)
	Menopausal status (pre- or postmenopausal)
	History of subfertility? Yes/no
	History of ovarian stimulation for subfertility? Yes/no
For ALL path	ents before menopause two extra questions pop up:

Patient is currently pregnant? (No/Yes)

Patient became pregnant during the last year? (No/Yes)

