 - o If surgery was >120 days after the inclusion visit, but subjective assessment was not always probably or certainly malignant (including borderline) at every visit: classify as *uncertain (U1)*

- B. The tumor spontaneously resolved at any point during follow-up: classify as *benign*

- C. The patient did not receive surgery, the tumor did not resolve, and the last follow-up visit was ≥ 10 months after the inclusion visit:

- If subjective assessment was consistently labeled as probably or certainly benign during the first 14 months of follow-up (specific definition: subjective assessment was benign at the earliest visit after ≥ 10 months of follow-up, and subjective assessment was benign at all visits up to 14 months of follow-up): classify as *benign (B2)*
- If subjective assessment was consistently labeled as probably or certainly malignant (including borderline) during first 14 months of follow-up (specific definition: subjective assessment was borderline/malignant at the earliest visit after ≥ 10 months of follow-up, and subjective assessment was borderline/malignant at all visits up to 14 months of follow-up): classify as *malignant (M3)*
- Else, subjective assessment was inconsistent/uncertain during the first 14 months of follow-up: classify as *uncertain (U2)*

D. Other cases: classify as *uncertain*

- Patients that received follow-up of less than 10 months, without receiving surgery or experiencing spontaneous resolution of the tumor. Reasons for such short follow-up can be death, withdrawal from the study, or being lost to follow-up. (U3)
- Patients for which we did not have information after the inclusion visit. Reasons for such short follow-up can be death, withdrawal from the study, or being lost to follow-up. (U4)

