1.5 Statistical methods

1.5.1 Missing values for CA125 and outcome

CA125 was not mandatory in IOTA5, although it was highly encouraged. We expect missing values for CA125, for the following two reasons. First, following local protocols some centres were more committed than others to measure CA125. Second, the need to measure CA125 may depend on the overall clinical picture and the appearance of the tumour on ultrasound. Hence we expected clearly more missing values for cases that were followed up conservatively.

For some cases, as outlined above, the outcome is uncertain. The largest groups are cases without any information since the inclusion scan (U4 in the overview above), and cases with last FU <10 months after inclusion and without having had surgery and where the mass did not resolve spontaneously (U3).

Simply omitting cases with missing CA125 or outcome is likely to cause bias. For example, based on data from earlier IOTA studies, patients with missing CA125 have more often a benign tumor. The current data from IOTA5 indicate that CA125 is more often missing for patients that are followed conservatively than for patients that received surgery without follow-up visit. Further, we assume that conservatively followed patients with last follow-up <10 months will very often have a benign tumor.

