1.5.2 How to deal with patients with uncertain outcome in the analysis

The outcome is a part of the imputation procedure described above, hence we have imputed values. The primary analysis is based on the multiply imputed values for CA125 and the outcome (cf de Groot, 2011).

As described below, we will also perform a sensitivity analysis after omitting patients with an uncertain outcome, and a sensitivity analysis after imputation of the outcome for patients where the outcome was labelled as uncertain, or was derived using information on subjective assessment (groups B2, M2, M3, U1, U2, U3, U4).

Note that models including CA125 (RMI and ADNEX with CA125) will always be analysed using imputed data for CA125, even when patients with uncertain outcome are omitted. Hence, only when evaluating models without CA125 based on patients for which the outcome is not labelled as uncertain, we do not have to use multiply imputed data.

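### No planned analysis varies, in a controlled way, the assumption that unverified women (U3, U4) have the same malignancy odds as verified women with the same inclusion findings

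*SAP*

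**What the plan says.** All references are to the SAP part dated 28 May 2019 unless stated.

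- **Who is uncertain.** Section 1.3 defines U3 as "Patients that received follow-up of less than 10 months, without receiving surgery or experiencing spontaneous resolution of the tumor" and U4 as "Patients for which we did not have information after the inclusion visit". For both it names death, withdrawal and loss to follow-up as possible reasons. Section 1.5.1 calls these two the largest uncertain groups.
- **Primary analysis.** Section 1.5.1 sets uncertain outcomes to missing and imputes them by fully conditional specification (100 imputations). The variables are inclusion-scan findings, patient characteristics, type of center and CA125. Section 1.5.2 confirms: "The primary analysis is based on the multiply imputed values for CA125 and the outcome".
- **Stated view of the missing women.** Section 1.5.1 warns: "Simply omitting cases with missing CA125 or outcome is likely to cause bias". It adds: "we assume that conservatively followed patients with last follow-up <10 months will very often have a benign tumor".
- **Outcome checks.** Section 1.5.8 lists two. One is a "Sensitivity analysis where patients with an uncertain outcome as listed above (groups U1-U4 from section 1.3) are excluded rather than imputed". The other imputes U1-U4 together with the groups labelled from subjective assessment (B2, M2 and M3 in section 1.5.2; section 1.5.8 prints N2 where M2 is evidently meant). For both, the stated outputs are c-statistics and calibration curves.

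**The concern.** The SAP does not use the term missing at random, but imputation of this kind with no offset and no term for verification status implies it. A woman in U3 or U4 receives the malignancy odds of verified women with the same imputation variables. Inclusion data alone cannot test this. The SAP says it expects women with short follow-up to be mostly benign. Its own reasons for missing outcomes include death and loss, which need not be unrelated to malignancy once the inclusion scan is accounted for.

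A sensitivity analysis should vary the assumption in doubt. One planned check removes the women concerned. The other imputes them again with no stated departure from the assumption. If all three analyses agree, a reader may conclude that the results are robust to unverified outcomes, and that would be only weakly supported. The measures most exposed are sensitivity at the risk cut-offs, calibration and net benefit, because each depends on how many masses that look low-risk prove malignant.

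**Working it through.** **No plan figure to reproduce.** The Protocol says "This is an observational study and therefore a sample size cannot be calculated" and gives only a recruitment aim: "We aim to collect at least 3000 women with an adnexal mass". Neither document gives counts for U1-U4. The check is therefore a reading of the sections, followed by an illustration of size.

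**Reading**

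| Analysis | U3/U4 women | Malignancy odds given inclusion findings |
|---|---|---|
| Primary (1.5.1, 1.5.2) | imputed | same as verified women |
| Omission (1.5.8) | removed | not addressed |
| Wider imputation (1.5.8) | imputed, smaller reference set | same as the remaining verified women |

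The other analyses do not fill the gap. The management subgroups in 1.5.7 vary no outcome assumption, and the all-center analysis in 1.5.8 is confined to masses operated within 120 days. No offset, pattern-mixture, best/worst-case or tipping-point analysis appears.

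**Illustration A: sensitivity of one model**

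Inputs: N = 3,000 (Protocol aim; it cancels out of the result). All the others are assumptions: uncertain share f = 10% or 20%; 18% malignant among verified women; model sensitivity 92% in verified malignancies and s = 50% or 70% in malignancies among U3/U4; malignancy rate in U3/U4 p = 3% or 5% under the primary assumption; odds multiplier k.

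- M = 0.18 × N × (1 − f)
- p′ = k·p / (1 − p + k·p)
- m = N × f × p′
- Sensitivity = (0.92·M + s·m) / (M + m)

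Smallest effect (f = 10%, p = 3%, s = 70%):
- M = 486.
- k = 1: m = 9.0, sensitivity 91.60%.
- k = 2: p′ = 5.83%, m = 17.5, sensitivity 91.24%. Loss 0.4 points.
- k = 4: p′ = 11.01%, m = 33.0, sensitivity 90.60%. Loss 1.0 point.

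Largest effect (f = 20%, p = 5%, s = 50%):
- M = 432.
- k = 1: m = 30.0, sensitivity 89.27%.
- k = 2: p′ = 9.52%, m = 57.1, sensitivity 87.09%. Loss 2.2 points.
- k = 4: p′ = 17.39%, m = 104.3, sensitivity 83.83%. Loss 5.4 points.

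With all U3/U4 benign, sensitivity is 92.0%. Omission also returns 92.0% in this set-up, whatever the true rate in U3/U4. At f = 5%, fourfold odds cost 0.5-1.4 points.

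**Illustration B: a different model**

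Assumptions: calibrated risk with logit distributed Normal(−2.9, 2.6), giving 17.7% malignancy; probability of an uncertain outcome proportional to (1 − risk)². At equal conditional odds the AUC is 0.913, sensitivity at the 10% cut-off is 0.914 and observed/expected is 1.00.

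| Uncertain share | Odds ratio | AUC | Sensitivity at 10% | Observed/expected |
|---|---|---|---|---|
| 5% | 4 | 0.907 | 0.904 | 1.03 |
| 10% | 2 | 0.909 | 0.907 | 1.03 |
| 10% | 4 | 0.902 | 0.895 | 1.06 |
| 20% | 0.25 | 0.919 | 0.925 | 0.95 |
| 20% | 2 | 0.905 | 0.900 | 1.05 |
| 20% | 4 | 0.894 | 0.877 | 1.12 |

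Fourfold odds lower the AUC by 0.006-0.019. Sensitivity falls by about 1, 2 or 4 points at 5%, 10% or 20% uncertain. Even at equal conditional odds, the crude malignancy rate is 7% in uncertain women against 18-20% in verified women.

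**The case against.** The strongest points on the other side are these.

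1. **The imputation already lets crude rates differ.** It conditions on about 20 inclusion variables plus CA125, including six-level certainty, ascites, metastases and color score. This stands. Only a difference beyond those variables is untested.
2. **The wider imputation is more than a repeat.** Removing B2 shrinks the benign part of the reference set. If B2 is a share b of verified benign women in a stratum, and M2 and M3 are negligible, the malignancy odds there are multiplied by 1/(1 − b): 2 at b = 50%, 4 at b = 75%. The documents do not give b. This stands in part: the analysis can move the imputed U3/U4 rate, but the shift is not chosen or reported, and B2 is re-imputed at the same time.
3. **Center selection limits the problem.** Section 1.3 confines the main analysis to 17 centers described as having good follow-up and surgery data. The follow-up plan of 27 December 2017 selected its centers partly on the share with an observed outcome or at least 10 months of follow-up, nearly the complement of U3/U4. This stands, and the 10-20% share used above may be too high.
4. **Omission as a labelled secondary contrast is not a contradiction**, and the expectation of benign outcomes is an argument against omission, not an input to the imputation. Both are fair.

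A reader might infer that the planned checks leave the safety of low-risk predictions, or the ranking of the methods, in doubt. The documents do not support that. The SAP makes no such safety claim: its net benefit concerns referral to oncological care at thresholds of 5-50%, and section 1.1 says this is not a true validation study. Nothing here computes a ranking; the illustrations evaluate one hypothetical model, and all methods are compared on the same imputed outcomes.

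**Conclusion.** The gap is real but moderate. The primary analysis assumes equal malignancy odds for verified and unverified women with the same inclusion findings, and no planned analysis varies this by a stated amount. Agreement among the three analyses would be limited evidence, not proof, of robustness.

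The size cannot be established from the documents. With the other inputs held fixed and 10-20% uncertain, doubling the odds costs about 0.4-2.2 points of sensitivity and fourfold odds about 1.0-5.4 points. The upper figures need every unfavourable input at once. The AUC changes little, so the c-statistic is the reported measure least likely to reveal a problem. If U3 and U4 are few, the effect is small. This is a worthwhile, inexpensive addition, not a defect that invalidates the primary analysis.

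**What to change.** Add one delta-adjusted imputation analysis to section 1.5.8:

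- For U3 and U4 only, multiply the odds of any malignant category versus benign by 0.5, 2 and 4 in the imputation step, with the same multiplier for all four malignant categories.
- Add a run in which all U3/U4 women are benign. Do this by forced assignment, since a multiplier of 0 has no finite log-odds offset.
- For each run report the c-statistic, sensitivity and specificity at the planned cut-offs, calibration and net benefit.
- Report the number of women in U3 and U4, and note any multiplier at which a comparison between methods changes.

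The cost is a few reruns of the existing imputation code, some care in applying the offset to a five-category outcome, and one supplementary table. The stated range of results may become wider.
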